9.2.7 Time and Dose Considerations

Fractionation: Patients will receive 1 treatment per day, 5 days per week. All fields will be treated each day. At least 2 fractions must be given during the first week of treatment.

9.2.8 Treatment Technique

Any 3D treatment technique which delivers the appropriate dose to the PTV is permitted. Coplanar and noncoplanar techniques are both allowed, but attention should focus on use of multiple nonoverlapping treatment fields according to optimal standard of care which will also generally reduce skin dose. A treatment planning computed tomography (CT) scan is required. The MRI-defined volumes should be superimposed onto the treatment planning CT.

9.2.9 Simulation

Simulation will be performed using a CT simulator. As the intent is treatment with the tumor-treating field (TTF) array applicator in place, simulation with a standard Aquaplast mask placed over the applicator and the head shaved. At the time of simulation, an additional simulation mask preparation and scan will be performed without the transducer arrays in place. The purpose is to ensure prompt transition to an optimal RT plan with an appropriately immobilization mask should treatment be required to continue without the TTF array in place.

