SoA	Schedule of Assessments
SRC	Safety Review Committee
STAT-3	signal transducer and activator of transcription 3
SUSAR	suspected unexpected serious adverse reaction
TITE-BOIN	time-to-event Bayesian optimal interval
THC	tetrahydrocurcumin
TIW	ter in week (three times weekly)
T _{max}	time to maximum plasma concentration
TMZ	temozolomide
TNF	tumor necrosis factor
TTF	tumor=treating field
ULN	upper limit of normal
VEGF	vascular endothelial growth factor
WHODrug	World Health Organization Drug Dictionary
WNT	wingless and INT-1
WOCBP	women of childbearing potential
WSTFT	weighted standardized follow-up time

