4.2 Scientific Rationale for Study Design

Administration of CRT is the standard of care for patients with HGG. In this study, LC will be used in combination with standard therapy.

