5.9.1 Prohibited Therapies

No investigational or commercial agents or therapies may be used during the study to treat the patient's malignancy other than those specified by this protocol.

In addition, the following commonly-used drugs and drug classes are not permitted during the study:

- Levofloxacin
- Penicillins
- Cephalosporins
- Ibuprofen (patients should also be instructed not to take this medication at home)
- Methyldopa
- Quinidine

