9.2.10 Patient Position and Immobilization

Immobilization devices such as Thermoplastic mask should be used for all patients.

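### Section 9.2.9 has radiotherapy simulated and delivered with a tumor-treating-field array in place, although that device is not part of the study regimen

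*Protocol*

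**What the plan says.** Section 9.2.9 of the Protocol gives the simulation instructions for RT. After a sentence requiring a CT simulator, it states the premise "As the intent is treatment with the tumor-treating field (TTF) array applicator in place" and calls for "simulation with a standard Aquaplast mask placed over the applicator and the head shaved". It adds that "an additional simulation mask preparation and scan will be performed without the transducer arrays in place", so that a plan is ready if treatment has to go on without the array. The array is thus the default and its absence the fallback.

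The neighbouring sections cover ordinary planning without mention of a device. Section 9.2.8: "A treatment planning computed tomography (CT) scan is required". Section 9.2.10: "Immobilization devices such as Thermoplastic mask should be used for all patients".

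The only other mention of TTF is the entry "tumor=treating field" in section 1.4. Section 4.2 describes the regimen in these terms: "In this study, LC will be used in combination with standard therapy". The standard therapy is RT and temozolomide (TMZ), and LC is liposomal curcumin. Section 5.9.1 says "No investigational or commercial agents or therapies may be used during the study to treat" the patient's cancer, with an exception for those the protocol specifies.

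**The concern.** The planning appendix and the treatment sections describe different treatments. Under Table 5 a patient receives LC, TMZ and RT in the concurrent period. Under 9.2.9 the same patient is simulated and irradiated with an antitumor device on the scalp. A site cannot satisfy both as written, and section 7 says that waivers are not allowed.

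Two things are at stake. If the device is not intended, patients are told to have their heads shaved and to undergo a second simulation for no study purpose. If a site takes 9.2.9 at its word, an unlisted modality enters the period in which the primary endpoint, the number of DLTs, is observed, and it also bears on the secondary endpoints of overall and progression-free survival by dose level.

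**Working it through.** No figure in the protocol depends on TTF, so there is nothing to reproduce. The check sets the relevant sections side by side.

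**1. Where TTF appears.** Section 9.2.9 (three of its four sentences) and the abbreviation list in 1.4. Nowhere else.

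**2. Where a device used during RT would be expected.**

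| Place | Treatments covered | TTF |
|---|---|---|
| 4.1 Overall Design | LC, RT, TMZ | absent |
| 4.1.3 Administration of Study Therapies | LC with chemoradiotherapy (CRT), then with adjuvant TMZ | absent |
| Table 5, concurrent period | LC, TMZ, RT | absent |
| 5.1, inclusion criterion 4 | TMZ and RT for 6 weeks | absent |
| 7.2.1.2, adverse event attribution | LC, TMZ, RT | absent |

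Table 5 is the regimen table that matters. Tables 6 and 7 cover periods without RT, and Table 4 is the dose-escalation schedule.

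**3. Is 9.2.9 operative?** Yes. Section 5.5.4 refers sites to 9.2 for treatment planning, and 9.1.9 provides for record review to confirm that treatment followed the protocol.

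**4. If TTF is not intended.** Sections 9.2.8 and 9.2.10 require one planning CT and one immobilization mask. Section 9.2.9 as written asks for two masks and two scans. The excess is 2 − 1 = 1 mask and 1 scan per patient, plus the shaving.

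**5. If 9.2.9 is followed in full.** The DLT window in 4.1.1 is 6 weeks with CRT plus 4 weeks of LC alone, 10 weeks in all. RT is given Monday to Friday.
- 30 fractions (9.2.2): 30 / 5 = 6 weeks, or 6 / 10 = 60% of the window.
- 33 fractions (the upper end in 4.1): 33 / 5 = 6.6 weeks, or 6.6 / 10 = 66%.

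This assumes that the array is worn throughout RT. The protocol gives no TTF schedule or duration.

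**6. Would a device toxicity count as a DLT?** Section 4.1.1 counts grade 3 and 4 nonhematological, non-CNS toxicities, subject to listed exceptions, and sets no requirement that the event be related to LC. A qualifying device toxicity would therefore count. Table 10 shows how little is needed to matter: with 3 evaluable patients and none pending, 0 DLTs means escalate, 1 means stay and 2 means de-escalate. One additional event can change the decision.

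**7. Size of the effect.** It cannot be calculated. The protocol gives no rate of TTF use and no device toxicity rate.

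**The case against.** The strongest reply is that these are three apparently stray sentences in a planning appendix. Everything that defines the treatment omits TTF, so sensible sites would ignore them, and no dose rule, endpoint or population is shown to change. Much of this stands: the natural reading is that TTF is not a study therapy, and on that reading no analysis is affected. But 9.2.9 is current text that tells staff what to do to patients, and a statistical analysis plan cannot correct it.

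Several stronger readings are tempting, and the protocol does not support them.

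- **That 9.2.9 directly violates 5.9.1.** Section 5.9.1 exempts what the protocol specifies, and 9.2.9 is protocol text. If 9.2.9 specifies TTF, 5.9.1 does not bar it; if it does not, 5.9.1 does. The defect is that the reader cannot tell which.
- **That the applicator simulation is impossible.** The protocol does not say whether the sites have the device.
- **That the missing attribution category would distort DLT counts.** DLTs are defined without an attribution test, so the category would not change what counts. Table 17 also lets investigators weigh concomitant therapy as an alternative cause.
- **That the exposure summary in 8.4.3 is a second defect.** It concerns study treatments, and leaving out a device that is not one is to be expected.
- **That the text was carried over from another protocol.** It may have been, but nothing in the document shows this.

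**Conclusion.** The conflict between 9.2.9 and the study regimen holds. It is more than clerical, because following the text changes what is done to patients. If TTF is not intended, the cost is shaving and one extra mask and scan per patient. If the text is followed in full, an unlisted device is worn for about 6 to 6.6 of the 10 DLT weeks, assuming wear throughout RT, and a qualifying toxicity from it would count towards the dose decision. A reader might infer that dose finding is compromised. The document does not support that: the route exists, but its size cannot be derived and nothing shows that TTF would actually be used. Severity is minor to moderate.

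**What to change.** The sponsor first confirms that TTF is not intended. Then:

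- Replace the three TTF sentences in 9.2.9 with a single standard CT simulation using an immobilization mask, consistent with 9.2.8 and 9.2.10.
- Delete the TTF entry in 1.4.

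After that the general bar in 5.9.1 covers TTF, and naming it there is optional. The cost is one confirmation and a short wording change, with no effect on design or analysis.

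Only if TTF is intended during RT should it be added to Table 5, with exposure recording and an adverse event attribution category. Nothing in 9.2.9 supports extending it to Tables 6 and 7.

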9.2.10 Patient Position and Immobilization

Immobilization devices such as Thermoplastic mask should be used for all patients.

9.2.11 Field Shaping

Field shaping can be done with blocks or multileaf collimation.

9.2.12 Isocenter Verification

The equivalent of orthogonal (anteroposterior and lateral) digitally reconstructed radiographs (DRRs) and corresponding orthogonal weekly portal images (film or electronic) are required. Alternatively, image guidance with kilovoltage imaging and setup DRRs or cone beam CT is acceptable.

9.3 Appendix 3: Clinical Laboratory Tests

- The tests detailed in [Table 12](#) will be performed.
- Protocol-specific requirements for inclusion or exclusion of patients are detailed in [Section 5](#) of the protocol.
- Additional tests may be performed at any time during the study as determined necessary by the Investigator or required by local regulations.
- Pregnancy testing

Table 12. Protocol-Required Safety Laboratory Assessments

Laboratory Assessments	Parameters
Hematology	Hgb Hematocrit RBC count RBC indices: MCV MCH % reticulocytes WBC count with differential: Neutrophils Lymphocytes Monocytes Eosinophils Basophils Platelet count
Clinical Chemistry	Sodium Potassium Calcium Total and direct bilirubin BUN Creatinine Glucose (may be performed without fasting) Total Protein Alkaline phosphatase AST /SGOT ALT / SGPT LDH Phosphorus
Routine Urinalysis	Specific gravity Dipstick: pH Glucose Protein Blood Ketones Bilirubin Urobilinogen Nitrite Leukocyte esterase Microscopic examination (if blood or protein is abnormal)
Other Screening Tests	Urine human chorionic gonadotropin (hCG) pregnancy test (as needed for WOCBP)

ALT = alanine aminotransferase; AST = aspartate aminotransferase; BUN = blood urea nitrogen; hCG = human chorionic gonadotropin; LDH = lactate dehydrogenase; MCV = mean corpuscular volume; MCH = mean corpuscular hemoglobin; RBC = red blood cell; SGOT = serum glutamic-oxaloacetic transaminase; SGPT = serum glutamic-pyruvic transaminase; WBC = white blood count; WOCBP = women of childbearing potential)

Investigators must document their review of each laboratory safety report.

9.4 Appendix 4: Adverse Events: Definitions and Procedures for Recording, Evaluating, Follow-up, and Reporting

9.4.1 Definition of Adverse Event

Table 13. Definition of Adverse Event

AE Definition

• An AE is any untoward medical occurrence in a patient or clinical study patient, temporally associated with the use of study intervention, whether or not considered related to the study intervention.• NOTE: An AE can therefore be any unfavorable and unintended sign (including an abnormal laboratory finding), symptom, or disease (new or exacerbated) temporally associated with the use of study intervention.

Table 14. Events Meeting the Adverse Event Definition

Events Meeting the AE Definition

• Any abnormal laboratory test results (hematology, clinical chemistry, or urinalysis) or other safety assessments (eg, ECG, radiological scans, vital signs measurements), including those that worsen from baseline, considered clinically significant in the medical and scientific judgment of the Investigator (ie, not related to progression of underlying disease).• Exacerbation of a chronic or intermittent pre-existing condition including either an increase in frequency and/or intensity of the condition.• New conditions detected or diagnosed after study intervention administration even though it may have been present before the start of the study.• Signs, symptoms, or the clinical sequelae of a suspected drug-drug interaction.• Signs, symptoms, or the clinical sequelae of a suspected overdose of either study intervention or a concomitant medication. Overdose per se will not be reported as an AE/SAE unless it is an intentional overdose taken with possible suicidal/self-harming intent. Such overdoses should be reported regardless of sequelae.• “Lack of efficacy” or “failure of expected pharmacological action” per se will not be reported as an AE or SAE. Such instances will be captured in the efficacy assessments. However, the signs, symptoms, and/or clinical sequelae resulting from lack of efficacy will be reported as AE or SAE if they fulfill the definition of an AE or SAE.• The signs, symptoms, and/or clinical sequelae resulting from lack of efficacy will be reported as AE or SAE if they fulfill the definition of an AE or SAE. Also, “lack of efficacy” or “failure of expected pharmacological action” also constitutes an AE or SAE.

9.4.2 Definition of Serious Adverse Event

If an event is not an AE per definition above, then it cannot be an SAE even if serious conditions are met (eg, hospitalization for signs/symptoms of the disease under study, death due to progression of disease).

Table 15. Definition of Serious Adverse Event

A SAE is defined as any untoward medical occurrence that, at any dose:
a. Results in death
b. Is life-threatening The term 'life-threatening' in the definition of 'serious' refers to an event in which the patient was at risk of death at the time of the event. It does not refer to an event, which hypothetically might have caused death, if it were more severe.
c. Requires inpatient hospitalization or prolongation of existing hospitalization In general, hospitalization signifies that the patient has been detained (usually involving at least an overnight stay) at the hospital or emergency ward for observation and/or treatment that would not have been appropriate in the physician's office or outpatient setting. Complications that occur during hospitalization are AEs. If a complication prolongs hospitalization or fulfills any other serious criteria, the event is serious. When in doubt as to whether "hospitalization" occurred or was necessary, the AE should be considered serious. Hospitalization for elective treatment of a pre-existing condition that did not worsen from baseline is not considered an AE.
d. Results in persistent disability/incapacity The term disability means a substantial disruption of a person's ability to conduct normal life functions. This definition is not intended to include experiences of relatively minor medical significance such as uncomplicated headache, nausea, vomiting, diarrhea, influenza, and accidental trauma (eg, sprained ankle) which may interfere with or prevent everyday life functions but do not constitute a substantial disruption.
e. Is a congenital anomaly/birth defect
f. Other situations: Medical or scientific judgment should be exercised in deciding whether SAE reporting is appropriate in other situations such as important medical events that may not be immediately life-threatening or result in death or hospitalization but may jeopardize the patient or may require medical or surgical intervention to prevent one of the other outcomes listed in the above definition. These events should usually be considered serious. Examples of such events include invasive or malignant cancers, intensive treatment in an emergency room or at home for allergic bronchospasm, blood dyscrasias or convulsions that do not result in hospitalization, or development of drug dependency or drug abuse. Examples of such events include invasive or malignant cancers, intensive treatment in an emergency room or at home for allergic bronchospasm, blood dyscrasias or convulsions that do not result in hospitalization, or development of drug dependency or drug abuse.

9.4.3 Recording and Follow-Up of Adverse Events

Table 16. Recording and Follow-Up of Adverse Events

AE and SAE Recording

• When an AE/SAE occurs, it is the responsibility of the Investigator to review all documentation (eg, hospital progress notes, laboratory reports, and diagnostics reports) related to the event.• The Investigator will then record all relevant AE/SAE information in the CRF.• It is not acceptable for the Investigator to send photocopies of the patient’s medical records to the Sponsor in lieu of completion of the /AE/SAE CRF page.• The Investigator will attempt to establish a diagnosis of the event based on signs, symptoms, and/or other clinical information. Whenever possible, the diagnosis (not the individual signs/symptoms) will be documented as the AE/SAE.
Assessment of Intensity

The Investigator will make an assessment of intensity for each AE and SAE reported during the study and assign it to 1 of the following categories:
 
• Mild: An event that is easily tolerated by the patient, causing minimal discomfort and not interfering with everyday activities.• Moderate: An event that causes sufficient discomfort and interferes with normal everyday activities.• Severe: An event that prevents normal everyday activities. An AE that is assessed as severe should not be confused with a SAE. Severe is a category utilized for rating the intensity of an event; and both AEs and SAEs can be assessed as severe. 
An event is defined as ‘serious’ when it meets at least 1 of the predefined outcomes as described in the definition of an SAE, NOT when it is rated as severe.
 
Other measures to evaluate AEs and SAEs may be used (eg, CTCAE).

Table 17. Assessment of Causality

Assessment of Causality

• The Investigator is obligated to assess the relationship between study intervention and each occurrence of each AE/SAE.• A “reasonable possibility” of a relationship conveys that there are facts, evidence, and/or arguments to suggest a causal relationship, rather than a relationship cannot be ruled out.• The Investigator will use clinical judgment to determine the relationship.• Alternative causes, such as underlying disease(s), concomitant therapy, and other risk factors, as well as the temporal relationship of the event to study intervention administration will be considered and investigated.• The Investigator will also consult the Investigator’s Brochure and/or Product Information, for marketed products, in their assessment.• For each AE/SAE, the Investigator must document in the medical notes that they have reviewed the AE/SAE and has provided an assessment of causality.

- There may be situations in which an SAE has occurred and the Investigator has minimal information to include in the initial report to the Sponsor. However, **it is very important that the Investigator always make an assessment of causality for every event before the initial transmission of the SAE data to the Sponsor.**
- The Investigator may change their opinion of causality in light of follow-up information and send a SAE follow-up report with the updated causality assessment.
- The causality assessment is one of the criteria used when determining regulatory reporting requirements.

Table 18. Follow-Up of Adverse Events

Follow-Up of AEs and SAEs

• The Investigator is obligated to perform or arrange for the conduct of supplemental measurements and/or evaluations as medically indicated or as requested by the Sponsor to elucidate the nature and/or causality of the AE or SAE as fully as possible. This may include additional laboratory tests or investigations, histopathological examinations, or consultation with other health care professionals.• If a patient dies during participation in the study or during a recognized follow-up period, if available, the Investigator will provide the Sponsor with a copy of any postmortem findings including histopathology.• New or updated information will be recorded in the originally completed CRF.• The Investigator will submit any updated SAE data to the Sponsor within 24 hr of receipt of the information.

9.4.4 Reporting of Serious Adverse Events

Table 19. Recording of Serious Adverse Events

SAE Reporting to Sponsor via an Electronic Data Collection Tool

• The primary mechanism for reporting an SAE to the Sponsor will be the electronic data collection tool.• The site will enter the SAE data into the electronic system as soon as it becomes available.• After the study is completed at a given site, the electronic data collection tool will be taken off-line to prevent the entry of new data or changes to existing data.• Any AE that meets a protocol-defined criterion as an SAE must be submitted within 24 hours of site awareness on an SAE form to [contact].

9.5 Appendix 5: Contraceptive Guidance and Collection of Pregnancy Information

The effects of LC on the developing human fetus are unknown, but possible teratogenic effects have been observed in animal and in vitro models. For this reason and because LC agents as well as other therapeutic agents (TMZ) used in this trial are known to be teratogenic, WOCBP and men must agree to use adequate contraception (hormonal or barrier method of birth control; abstinence) prior to study entry and for the duration of study participation. Should a woman become pregnant or suspect she is pregnant while

she or her partner is participating in this study, she should inform her treating physician immediately. Men treated or enrolled in this study must also agree to use adequate contraception prior to the study, for the duration of study participation, and for 4 months after completion of LC administration.

Pregnant women are excluded from this study because the curcuminoid moiety of LC has the potential for teratogenic or abortifacient effects at high doses. Mouse studies using high-dose curcumin have suggested lower fetal birth weights ([Chen et al, 2010](#); [Ganiger et al, 2007](#)), and pegylated curcumin is associated with reduced live birth rates in mature females (Murphy et al, 2012). The same study showed hastened onset of puberty in immature female mice, raising concerns for AEs in nursing infants of mothers treated with LC. Breastfeeding should be discontinued if a mother is being treated with LC. These potential risks also apply to other agents used in the study, including but not limited to the co-administration of TMZ, which is associated with embryo-fetal toxicity.

Women of Childbearing Potential

A woman is considered fertile following menarche and until becoming postmenopausal unless permanently sterile (see below).

If fertility is unclear (eg, amenorrhea in adolescents or athletes) and a menstrual cycle cannot be confirmed before first dose of study intervention, additional evaluation should be considered.

Women in the following categories are not considered WOCBP:

1. Premenarchal
2. Premenopausal female with 1 of the following:
 - Documented hysterectomy
 - Documented bilateral salpingectomy
 - Documented bilateral oophorectomy

For individuals with permanent infertility due to an alternate medical cause other than the above, (eg, mullerian agenesis, androgen insensitivity), Investigator discretion should be applied to determining study entry.

Note: Documentation can come from the site personnel's: review of the patient's medical records, medical examination, or medical history interview.

3. Postmenopausal female
 - A postmenopausal state is defined as no menses for 12 months without an alternative medical cause.
 - Females on hormonal replacement therapy (HRT) and whose menopausal status is in doubt will be required to use one of the nonestrogen hormonal highly effective contraception methods if they wish to continue their HRT

during the study. Otherwise, they must discontinue HRT to allow confirmation of postmenopausal status before study enrollment.

Collection of Pregnancy Information

Male patients with partners who become pregnant

- The Investigator will attempt to collect pregnancy information on any male patient's female partner who becomes pregnant while the male patient is in this study. This applies only to male patients who receive study intervention.
- After obtaining the necessary signed informed consent from the pregnant female partner directly, the Investigator will record pregnancy information on the appropriate form and submit it to the Sponsor within 24 hr of learning of the partner's pregnancy. The female partner will also be followed to determine the outcome of the pregnancy. Information on the status of the mother and child will be forwarded to the Sponsor. Generally, the follow-up will be no longer than 6 to 8 weeks following the estimated delivery date. Any termination of the pregnancy will be reported regardless of fetal status (presence or absence of anomalies) or indication for the procedure.

Female Patients who become pregnant

- The Investigator will collect pregnancy information on any female patient who becomes pregnant while participating in this study. Information will be recorded on the appropriate form and submitted to the Sponsor within 24 hr of learning of a patient's pregnancy.
- The patient will be followed to determine the outcome of the pregnancy. The Investigator will collect follow-up information on the patient and the neonate and the information will be forwarded to the Sponsor. Generally, follow-up will not be required for longer than 6 to 8 weeks beyond the estimated delivery date. Any termination of pregnancy will be reported, regardless of fetal status (presence or absence of anomalies) or indication for the procedure.
- While pregnancy itself is not considered to be an AE or SAE, any pregnancy complication or elective termination of a pregnancy will be reported as an AE or SAE. A spontaneous abortion is always considered to be an SAE and will be reported as such. Any poststudy, pregnancy-related SAE considered reasonably related to the study intervention by the Investigator will be reported to the Sponsor as described in [Section 7.2.5](#). While the Investigator is not obligated to actively seek this information in former study patients, they may learn of an SAE through spontaneous reporting.
- Any female patient who becomes pregnant while participating in the study must discontinue infusions of LC. Modification of standard CRT should be undertaken as per standard clinical practice; the Investigator should consult the Medical Monitor.

